4.4.1 Derivation

Individual concentrations below the LLOQ of the bioanalytical assay will be reported as NQ (Not Quantifiable) in the listings with the LLOQ defined in the footnotes of the relevant TFLs.

Individual concentrations that are Not Reportable will be reported as NR and those that are missing will be reported as NS (No Sample) in the listings. If more details are collected regarding the reasons for missing concentrations, the comment text will be displayed.

Concentrations that are NQ, NR or NS will be handled as follows for the provision of descriptive statistics:

- Any values reported as NR or NS will be excluded from the summary tables and corresponding figures.

- At a time point where less than or equal to 50% of the concentration values are NQ, all NQ values will be set to the LLOQ, and all descriptive statistics will be calculated accordingly.
- At a time point where more than 50% (but not all) of the values are NQ, the geometric mean, the gSD, geometric mean \pm gSD and geometric CV will be set to Not Calculable (NC). The maximum value will be reported from the individual data, and the minimum and median will be set to NQ.
- If all concentrations are NQ at a time point, no descriptive statistics will be calculated for that time point. The geometric mean, minimum, median and maximum will be reported as NQ and the geometric CV, gSD and geometric mean \pm gSD as NC.
- The number of values below LLOQ ($n < \text{LLOQ}$) will be reported for each time point together with the total number of collected values (n).
- Three observations $>$ LLOQ are required as a minimum for a plasma concentration to be summarized. Two observations $>$ LLOQ are presented as minimum and maximum with the other summary statistics as NC. One observation $>$ LLOQ is presented as maximum with the other summary statistics as NC.

4.5 Immunogenicity

Not Applicable.

4.6 Safety Analyses

The domain safety covers exposure, adverse events, clinical laboratory, vital signs, and ECG.

Tables are provided for the SAS unless otherwise specified, for baseline, on-treatment and on-study periods as defined in Section 3.3.1.3.

4.6.1 Exposure

4.6.1.1 Definitions and Derivations

Exposure data will be presented for the on-treatment period.

Duration of exposure will be presented for all strength of AZD0780, AZD0780 Total, Placebo and Total.

Exposure measured as amount administered will be presented for all strength of AZD0780, and AZD0780 Total.

Duration of exposure is calculated for participants in the SAS as the total number of days on study treatment and it is calculated as:

Duration of exposure (days) = $\min(\text{Last day of study treatment} + 10, \text{Last study visit}) - \text{first day of study treatment} + 1$

Last study treatment administration will be extracted from the EXL form, while the first dose administration is derived from the earliest administered dose collected on the EXL form. If any of the first or last dates are missing or partially missing, then imputed dates will not be used and study treatment exposure is set to missing.

Cumulative exposure is also computed using the following duration (days) categories:

- ≥ 14 days
- ≥ 28 days
- ≥ 56 days
- ≥ 84 days

These categories are cumulative, and participants will be included in all categories that apply to them.

Exposure as measured by amount administered will be calculated from the data collected on the DA form as:

$$\begin{aligned} m(\text{AZD0780}) [\text{mg}] \\ = \sum_{i=P_1}^{P_{\text{Last dispensing period}}} & ((n(\text{tablet dispensed}))_{\text{Bottle A}} \\ & - n(\text{tablet returned})_{\text{Bottle A}} * \text{dose(tablet)}_{\text{Bottle A}}) \\ & + ((n(\text{tablet dispensed}))_{\text{Bottle B}} - n(\text{tablet returned})_{\text{Bottle B}}) \\ & * \text{dose(tablet)}_{\text{Bottle B}} + ((n(\text{tablet dispensed}))_{\text{Bottle C}} \\ & - n(\text{tablet returned})_{\text{Bottle C}} * \text{dose(tablet)}_{\text{Bottle C}}) \end{aligned}$$

Where,

- $m(\text{AZD0780})[\text{mg}]$ – exposure to AZD0780 as measured by amount administered in milligrams
- $n(\text{tablet dispensed})_z$ – number of tablets dispensed in z at the beginning of given dispensing period
 - $z: \{\text{Bottle A, Bottle B, Bottle C}\}$
- $n(\text{tablet returned})_z$ – number of tablets returned in z at the end of given dispensing period
 - $z: \{\text{Bottle A, Bottle B, Bottle C}\}$
- dose(tablet)_z – dose of the tablet in z in a given day

- $z: \{Bottle\ A, Bottle\ B, Bottle\ C\}$
- P_x – dispensing period

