3.3.1.3 Definition of study periods

The following periods are defined in this study:

1. Screening

Start: Signing of the ICF

End: Day prior to first study treatment administration

2. On-treatment period

The on-treatment analysis period starts on the date of the first administration of study treatment and ends on the earliest of 10 days following the date of last dose of study treatment or the end of the on-study analysis period.

Start: Day of first study treatment administration

End: Day of last study treatment dose + 10 days

OR

End of on-study analysis period

Whichever occurs earlier

3. Follow-up period

Start: The day after the end of the treatment period

End: Last day in the study as recorded on the End of Study (EOS) form

4. On-study period

The on-study analysis period starts on the date of the first administration of study treatment and ends on the End of Study date as recorded on the EOS form, unless the participant dies while under follow-up, then the date of death is taken as the end of the on-study analysis period, as reported on the EOS form. No data should be collected after withdrawal of consent. If a participant withdraws consent to continue in the study, then the on-study analysis period ends on this date at the latest.

Start: Day of the first study treatment administration

End: Last day in the study as recorded on the End of Study (EOS) form

The allocation to the study periods is performed after the imputation of date as in Section 3.3.1.6.

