4.1.1 Subject Disposition and Completion Status

4.1.1.1 Definitions and Derivations

For disposition and completion status, the following definitions will apply:

- Subjects enrolled will be defined as a subject who signed the informed consent of the study.
- Subjects not randomised have consented to participate in the clinical study but are not subsequently randomly assigned to study intervention.
- Subjects randomised will be defined as a subject who has been randomised to a treatment group.
- Subjects randomised, not treated will be defined as a randomised subject who has not received any study treatment.
- Subjects who started treatment will be defined as a randomised subject who has received at least one dose of study treatment.
- Subjects who completed treatment will be defined as a subject who started treatment and has not permanently prematurely discontinued study treatment during the study. A subject who dies during participation without having permanently discontinued study treatment prior to date of death, will be considered to have completed treatment.
- Subjects who discontinued treatment will be defined as a subject who started treatment and has permanently prematurely discontinued study treatment for reasons other than death. The reasons for discontinuation as collected on the EOT eCRF will be presented. For reason collected as other, the specify field will be presented in listings but not in the disposition table.
- Subjects who completed study will be defined as a subject who has not withdrawn consent, has not been lost to follow-up and has not died.
- Subjects withdrawn from study will be defined as a subject who has withdrawn consent, has been lost to follow-up or died. The numbers for each of these categories will be presented.
- Subjects who discontinued treatment due to global/country situation, if applicable.
- Subjects who withdraw from study due to global/country situation, if applicable.

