4.1.9 Study Drug Compliance

4.1.9.1 Definitions and Derivations

Percent compliance to treatment will be calculated for each participant based on tablet count as: the number of tablets taken (dispensed minus returned), divided by the number of tablets expected to have been taken, multiplied by one hundred. The number of tablets expected to have been taken is defined as 1 tablet/bottle (3 tablets in total) multiplied by ‘date of last dose minus date of first dose plus one’. If the number of tablets dispensed, or the number of tablets returned, is missing for at least one observation for a participant, compliance is not calculated for that participant.

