4.6.1.2 Presentation

The duration of exposure and exposure as measured by amount administered will be summarized using descriptive statistics according to the group defined in Section 4.6.1.1. Duration of exposure will also be presented categorically by using the cumulative categories as described above. Exposure over time will be presented in a figure, with one line for each treatment group.

A listing with individual exposure to study treatment will be presented.

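### SAP 4.6.1.1 labels duration of exposure as days on study treatment, but the formula gives in effect the length of the on-treatment period (94 days against an 84-day dosing span for a completer)

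*SAP*

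**What the plan says.** SAP Section 4.6.1.1 opens with "Exposure data will be presented for the on-treatment period". It then describes the measure: "Duration of exposure is calculated for participants in the SAS as the total number of days on study treatment and it is calculated as". The formula is min(last day of study treatment + 10, last study visit) − first day of study treatment + 1. Cumulative categories of ≥14, ≥28, ≥56 and ≥84 days are built on duration. If the first or last dose date is missing or partial, exposure is set to missing. Section 4.6.1.2 adds: "Exposure over time will be presented in a figure, with one line for each treatment group".

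SAP Section 3.3.1.3 says that the on-treatment period "ends on the earliest of 10 days following the date of last dose of study treatment or the end of the on-study analysis period". The on-study period in turn "ends on the End of Study date as recorded on the EOS form", with separate provisions for death and for withdrawal of consent.

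For compliance, SAP Section 4.1.9.1 derives the expected tablets from "date of last dose minus date of first dose plus one", without a 10-day extension. The protocol's Schedule of Activities plans once-daily dosing from Day 1 through Day 84, with Visit 8 on Day 99.

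**The concern.** The label and the formula describe different quantities. A reader of the exposure table would take the figure as time on drug, yet it carries an undisclosed tail of up to 10 days after the last dose. The formula does not quite match the on-treatment period either, because it is capped at the last study visit and that period is capped at the end of the on-study period.

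Protocol Section 9.2 says that the sample size is driven by safety and tolerability, so exposure is a basic description of the safety database. At stake are the duration summary, the cumulative categories and possibly the exposure figure, since Section 4.6.1.2 does not say which quantity that figure plots.

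**Working it through.** **Inputs.** Planned dosing Day 1 to Day 84; visits nominally on Days 1, 8, 15, 29, 57, 85 and 99, with a ±3-day window (protocol Schedule of Activities). 375 randomized and about 15% discontinuing (protocol Section 9.2). The documents give no distribution of stopping days. I assume last-dose days L uniform over Days 1 to 83.

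**Three quantities** (first dose on Day 1):
- Span = last dose − first dose + 1.
- SAP 4.6.1.1 = min(last dose + 10, last visit) − first dose + 1.
- On-treatment period (SAP 3.3.1.3) = min(last dose + 10, end of on-study period) − first dose + 1.

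**Planned figure.** Span = 84 − 1 + 1 = 84 = 12 × 7, which reproduces the 12-week regimen.

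**Completer, last dose Day 84.**
- Visit 8 on Day 99: min(94, 99) − 1 + 1 = 94, an excess of 10. The result is the same for any Visit 8 in the SAP's Day 94–104 analysis window.
- No Visit 8, last visit Day 85: min(94, 85) − 1 + 1 = 85, an excess of 1.
- Visit 8 attended and a 7-day interruption: still 94, against 84 − 7 = 77 days dosed, an excess of 17.

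When the last visit is on or after the last dose, the excess over the span runs from 0 to 10 days.

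**Early stoppers and the categories.** 0.15 × 375 = 56.25 stoppers; 56.25 / 83 = 0.678 per last-dose day. If the cap does not bind, reported duration is L + 10, so these last-dose days reach a threshold that the span does not:

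| Category | Last-dose days counted in | Expected participants |
|---|---|---|
| ≥14 | 4–13 | 10 × 0.678 = 6.8 |
| ≥28 | 18–27 | 6.8 |
| ≥56 | 46–55 | 6.8 |
| ≥84 | 74–83 | 6.8 |

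If stoppers attend only the next scheduled visit, ≥14 is first met at L = 8 (6 × 0.678 = 4.1 participants) and the other three rows do not change. If they have no visit after the last dose, none is counted upward.

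**Completers with an early Week 12 visit.** Assume visit days uniform over Days 82–88 and last dose the day before. Visits on Days 82, 83 and 84 give last doses on Days 81, 82 and 83, which is 3 of 7 days. Completers number 0.85 × 375 = 318.75, and 3/7 × 318.75 = 136.6, about 137 of 319. With Visit 8 attended the formula gives 91, 92 or 93 days, so all count as ≥84 although their span is 81 to 83. Visit timing is not in the documents; the possible range is 0 to all.

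**Cap and understatement.**
- Last dose Day 50, last visit Day 29: min(60, 29) − 1 + 1 = 29, against a span of 50.
- Last dose Day 70, last visit Day 57, end of study Day 90: SAP 4.6.1.1 gives min(80, 57) = 57, the on-treatment period is min(80, 90) = 80, and the span is 70. Here the formula equals neither of the other two.

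**The case against.** The best defence is that the 10 days are deliberate. Exposure is presented for the on-treatment period, that period runs to 10 days after the last dose, and the formula is explicit enough to program. This stands as far as it goes: nothing is miscalculated. It does not make the label true, and the different cap means that the formula is not exactly that period.

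Several stronger readings are tempting but not supported:
- *That the formula often understates exposure.* Understatement needs a fully recorded last dose and no later visit, because incomplete dates set exposure to missing. Protocol Section 7.1 asks those who stop to attend an early discontinuation visit and then Visit 8. It is an edge case.
- *That early stoppers are hidden.* Disposition tabulates discontinuation separately: "The reasons for discontinuation as collected on the EOT eCRF will be presented". Milligrams administered and compliance rest on tablet counts, without the 10-day extension, and individual exposure is listed.
- *That Section 4.1.9.1 is a rival definition of exposure.* It uses the span only to derive expected tablets.
- *That the span is the true number of days on treatment.* It does not subtract interruptions, which the SAP foresees as an action taken for adverse events.
- *That efficacy or adverse-event results are affected.* The efficacy models and the participant-based adverse-event percentages do not use this duration.

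**Conclusion.** The mismatch is real and minor. For a completer on the planned schedule who attends Visit 8, 94 against 84 is exact and needs no assumption; so is the 10-day limit on the excess over the span. The category counts are illustrative. The figure of about 6.8 stoppers per category rests on 15% stopping uniformly over Days 1–83 and a cap that does not bind. The figure of about 137 completers rests on uniform Week 12 visit days, a last dose the day before, and attendance at Visit 8. The two groups add in the ≥84 category, so a count based on nominal visit days alone would miss the completers. They have, however, finished the protocol's treatment period, so their place in ≥84 is a matter of visit timing and does not mean that treatment was cut short.

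**What to change.** - Relabel the existing formula as *length of the on-treatment period (Section 3.3.1.3)*, and cap it at the end of the on-study period, as that section does.
- Add last dose date − first dose date + 1, labelled *first-to-last-dose span (interruptions not subtracted)*.
- State which of the two the cumulative categories and the exposure-over-time figure use.
- If the categories use the span, add a footnote that a Week 12 visit early in the window can put a completer just under 84 days. Leave the category boundaries as they are.

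The cost is one relabel, one aligned cap, one derived variable, one sentence and possibly one footnote. If the categories stay on the relabelled period length, their counts change only where the aligned cap does. If they move to the span, the completers with early visits drop below 84 days, which is why the footnote is needed.

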3.3.1.5 Definition of study treatment

Study treatment is defined as the randomly assigned study treatment. For details regarding the background lipid lowering statin therapy please refer to Section 5.1 and Appendix F of the latest approved CSP and the Statin eligibility memo.

The study treatment is dispensed in 3 bottles as represented in [Table 4](#). The participant is instructed to take 1 tablet/bottle/day. Treatment compliance is defined in Section [4.1.9](#).

Table 4 – Representation of the Drug Dispensing Scheme

	Bottle A	Bottle B	Bottle C
1 mg	AZD0780 1 mg	Placebo	Placebo
3 mg	AZD0780 1 mg	AZD0780 1 mg	AZD0780 1 mg
10 mg	AZD0780 5 mg	AZD0780 5 mg	Placebo
30 mg	AZD0780 20 mg	AZD0780 5 mg	AZD0780 5 mg
Placebo	Placebo	Placebo	Placebo

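### As printed, the SAP formula for milligrams of AZD0780 administered applies the tablet dose differently to Bottle B than to Bottles A and C; its brackets need checking

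*SAP*

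**What the plan says.** SAP section 4.6.1.1 plans two exposure measures: duration in days, and amount of drug. The amount is to be presented for each AZD0780 strength and for AZD0780 Total. On its derivation the SAP says: "Exposure as measured by amount administered will be calculated from the data collected on the DA form as". The equation that follows sums three bottle terms over the dispensing periods, and its legend defines the result as "exposure to AZD0780 as measured by amount administered in milligrams".

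The position of the closing brackets gives these terms:

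- Bottle A: dispensed − (returned × dose)
- Bottle B: (dispensed − returned) × dose
- Bottle C: dispensed − (returned × dose)

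Section 3.3.1.5 supplies the doses: "The study treatment is dispensed in 3 bottles as represented in" Table 4. For example, the rows for the two lowest doses read "1 mg AZD0780 1 mg Placebo Placebo" and "3 mg AZD0780 1 mg AZD0780 1 mg AZD0780 1 mg". Section 4.1.9.1 (compliance) takes the number of tablets taken to be dispensed minus returned. Section 4.6.1.2 plans descriptive statistics for the amount administered and a listing of individual exposure. The amendment history records that the section 4.6.1 formula was moved from the EXL form to the DA form on 18 November 2024.

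**The concern.** One quantity is written in two ways within a single equation, and only one of them can be right. In the Bottle A and C terms, milligrams are subtracted from a count of tablets. Two consequences follow if the equation is programmed literally:

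- A placebo bottle in position A or C (dose 0) adds every dispensed tablet to the total as if it were a milligram of AZD0780.
- An active bottle in position A or C is under-counted when its tablets are stronger than 1 mg.

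The high-dose arm is hit hardest, because its 20 mg tablet is in Bottle A. This is a dose-ranging study whose sample size is said to rest on safety and tolerability (Protocol section 9.2). A table of milligrams administered that is not ordered by dose would mislead a reader of the safety section.

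**Working it through.** The documents give no milligram exposure figure, so there is none to reproduce.

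**Inputs**

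- Dose per tablet in Bottles A/B/C (SAP Table 4, placebo taken as 0): 1/0/0, 1/1/1, 5/5/0 and 20/5/5 mg. These sum to 1, 3, 10 and 30 mg per day, as they should.
- 35 tablets per bottle (Protocol Table 1).
- Three dispensings (Protocol Table 1, and the Brief Summary in section 1.1).
- One tablet per bottle per day (SAP 3.3.1.5), Day 1 through Day 84 (Protocol Table 1).
- Assumptions: one bottle of each type per dispensing, and all unused tablets returned.

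Tablets dispensed per bottle type: D = 3 × 35 = 105. At full adherence 84 are taken, so returns are R = 105 − 84 = 21.

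**Formulas**

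- Literal: (D − R·dA) + (D − R)·dB + (D − R·dC)
- Consistent: (D − R)·(dA + dB + dC)

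**Full adherence (D = 105, R = 21)**

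| Arm | A | B | C | Literal total, mg | Consistent total, mg |
|---|---|---|---|---|---|
| 1 mg | 105 − 21 = 84 | 0 | 105 − 0 = 105 | 189 | 84 × 1 = 84 |
| 3 mg | 84 | 84 | 84 | 252 | 84 × 3 = 252 |
| 10 mg | 105 − 105 = 0 | 84 × 5 = 420 | 105 | 525 | 84 × 10 = 840 |
| 30 mg | 105 − 420 = −315 | 420 | 105 − 105 = 0 | 105 | 84 × 30 = 2520 |

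The 3 mg arm is right only because all its tablets are 1 mg.

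**Size of the error.** For a Bottle A or C term, literal minus consistent is (D − R·d) − (D − R)·d = D·(1 − d), so R cancels. Summed over A and C, the error is −D·(dA + dC − 2):

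- 1 mg: −105 × (−1) = +105 mg
- 3 mg: 0
- 10 mg: −105 × 3 = −315 mg
- 30 mg: −105 × 23 = −2415 mg

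**Ordering of the arms.** With D = 105 and R returns per bottle type, the literal totals are 210 − R, 315 − 3R, 735 − 10R and 735 − 30R mg for the 1, 3, 10 and 30 mg arms.

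| R | 1 mg | 3 mg | 10 mg | 30 mg |
|---|---|---|---|---|
| 0 | 210 | 315 | 735 | 735 |
| 10 | 200 | 285 | 635 | 435 |
| 19 | 191 | 258 | 545 | 165 |
| 21 | 189 | 252 | 525 | 105 |
| 25 | 185 | 240 | 485 | −15 |

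- 30 mg against 10 mg: equal at R = 0 and lower at every R above 0.
- 30 mg against 1 mg: 735 − 30R < 210 − R needs 29R > 525, so R of 19 or more.
- 30 mg negative: 30R > 735, so R of 25 or more.

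**Early stopping.** A 30 mg participant who stops after 10 days of the first period has 35 dispensed and 25 returned per bottle. The literal total is (35 − 500) + 10 × 5 + (35 − 125) = −505 mg. The consistent total is 10 × 30 = 300 mg.

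**The case against.** The strongest reply is that this may not be an error in the SAP at all. The point turns on where one bracket closes in a multi-line typeset equation that was converted from PDF to text, and there are signs of disturbance. In all three terms a bracket closes directly after the dispensed count, which the legend writes without it. Each term also opens with a double bracket, which would fit an intended ((dispensed − returned) × dose). The two odd terms, A and C, are the ones in which a line break falls between the dispensed and returned counts. Against this, the brackets balance in every term as shown, so a drafting slip is equally possible. The text alone cannot settle it, and this part of the objection stands.

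It is also fair that the intended rule can be inferred. The result is labelled in milligrams, Bottle B has the right form, section 4.1.9.1 defines tablets taken correctly, and a negative amount would probably be caught in checking. That lowers the chance of harm, but a stated derivation should not depend on the programmer overriding it.

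A reader might go further and infer that the 30 mg arm would always show less drug than the 1 mg arm. The documents do not support that: at 10 returns per bottle type the literal totals are 435 mg against 200 mg, and the reversal needs 19 or more. A reader might also infer that exposure, compliance or efficacy results in general are compromised. They are not. Duration of exposure is computed from dates, compliance has its own correct formula, and no efficacy or adverse event analysis uses the milligram amount.

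**Conclusion.** The point holds as an inconsistency in the formula as it reads, subject to checking the approved SAP. If the brackets are as shown, the literal amount is wrong by +105, 0, −315 and −2415 mg per participant in the 1, 3, 10 and 30 mg arms, so AZD0780 Total is wrong as well. The milligram figures assume 105 tablets dispensed per bottle type. Given that, the errors do not depend on how many tablets come back. The comparisons between arms additionally assume the same number returned for each bottle type and in each arm. On that basis the 30 mg arm never exceeds the 10 mg arm, and at full adherence it is the lowest of the four.

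The reach is small: one descriptive safety summary and any listing of the milligram amount. No hypothesis test or stated decision rule depends on it.

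**What to change.** Compare the equation in SAP section 4.6.1.1 with the approved document. If the brackets there already enclose the difference for all three bottles, nothing needs changing. If they are as shown, replace the three terms with one: the sum over dispensing periods and over Bottles A, B and C of (n dispensed − n returned) × dose per tablet, with the dose set to 0 for placebo bottles. At full adherence this gives 84, 252, 840 and 2520 mg, which is 84 times the daily dose in each arm and a convenient test case for the program. The check takes minutes and the correction is one line of the SAP, with no change to data collection or to any other analysis.
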